2. STUDY OBJECTIVES

2.1. Primary Objectives

The primary objectives of this study are to evaluate the safety and tolerability of KNX100 administered orally as a single and multiple ascending doses in healthy volunteers.

2.2. Secondary Objectives

The secondary objectives of this study are to determine:

1. The PK profile of ascending doses of KNX100 and its metabolites when administered as a single oral dose in healthy volunteers.
2. The PK profile of ascending doses of KNX100 and its metabolites when administered as multiple doses in healthy volunteers.
3. The PK profile of KNX100 and its metabolites when administered twice daily as multiple doses in healthy volunteers.

3. INVESTIGATIONAL PLAN

3.1. Overall Study Design and Plan

This is a Phase 1, FIH, single site, single treatment, 2-part, double blind, placebo controlled, randomized, single ascending dose (SAD)/multiple ascending dose (MAD) study designed to evaluate the safety and tolerability of KNX100 as compared to placebo. This study will enroll healthy volunteers.

The planned enrollment is approximately 64 male and female subjects. The total number of subjects will depend on the number of dose levels assessed in dose-escalation. Completed subjects will have received either KNX100 (active study drug) or placebo. Subjects who discontinue will be replaced to achieve the targeted number of evaluable subjects in each cohort.

Healthy subjects who meet all eligibility criteria will be sequentially enrolled and assigned to a single cohort in Cohorts 1-4 in Part A of the study or in Cohorts 1-3 in Part B of the study. Each cohort selected will evaluate 8 subjects; 6 subjects will be randomly assigned to receive KNX100, and 2 subjects will be randomly assigned to receive placebo. Each cohort will be enrolled sequentially, and the subsequent dose increase will be based on the Cohort Review Committee (CRC) evaluation of data known to date.

Additional cohorts may be added as required, based on safety profile and CRC authorization.

Part A (SAD) will initially dose 2 sentinel subjects (one with KNX100 and one with placebo) in Cohort 1. The center will review safety and tolerability up to and including the 48-hour timepoint for the sentinel subjects before dosing the remaining subjects in the dose cohort. The CRC will be informed and authorize the decision to continue with the remainder of the cohort dosing. Each subject will receive 1 dose, administered orally, of study drug. All subjects in each cohort will have their data, up to and including the 30 -hour postdose timepoint, evaluated for safety and tolerability by the CRC before opening the next dose cohort based on assessment of all available data. The dosing schedule may be extended if additional observations are needed at a particular cohort. In the absence of unacceptable AEs, the CRC may decide to open the next cohort before they have reviewed all data from all 8 evaluable subjects who have completed up to and including the 30-hour timepoint postdose.

Subjects will be housed in the clinic from Day -3 prior to study drug administration and will remain in-house for 30 hours postdose (Day 2) for PK and safety assessments.

[figure not shown]
Part B (MAD) will evaluate up to 3 doses based on doses established during Part A (SAD). Each subject will receive 7 doses of study drug, administered either once (Cohorts 1 and 2) or twice daily (Cohort 3). All subjects in each MAD cohort will have their AE, PK, and electroencephalography (EEG) data, acquired up to and including Day 8, evaluated for safety and tolerability by the CRC before opening the next higher dose cohort. Subjects will be housed in the clinic from Day -3 prior to study drug administration and will remain in-house for 24 hours post morning dose (Day 8) for PK and safety assessments.

The study will be comprised of 3 periods: Screening (up to 28 days); Treatment (1 day for the SAD subjects and 7 days for MAD subjects) and Follow-up. Subjects will have a follow-up visit 7 days after the last dose. As SAD dosing is a single dose on Day 1, follow-up will occur

on Day 7. MAD dosing involves either single daily dosing (Cohorts 1 and 2) or twice daily dosing (Cohort 3) on Days 1 to 7, with a follow-up visit occurring on Day 14.

The overall study design is summarized in Figure 1. Refer to Appendix 1 and Appendix 2 for a detailed schedule of assessments.

Figure 1 Study Phases and Activities

3.2. Rationale for Study Design and Control Group

Study Design: This study is a 2-part, single site, single treatment, double-blind, randomized, placebo-controlled, dose escalating study to assess the safety, tolerability, and PK of single and multiple ascending doses and twice daily dosing of KNX100 administered orally to healthy males and females. Investigators and subjects will be blinded to treatment; however, the site pharmacist will be unblinded. Members of the CRC will be blinded; however, specific members may be unblinded to enable evaluation of PK and safety data for dose escalation decisions if required.

The design of this study is typical of those used for FIH studies with a "dose leader" (sentinel) design to better manage the safety aspects of the study. A sentinel design will be implemented during Part A, (SAD), with 2 subjects being dosed on the first dosing day of each Cohort. Of these, one will receive KNX100, and one will receive placebo. Safety and tolerability will be reviewed for these 2 sentinel subjects by the site, and CRC, before dosing the remaining subjects in the dose cohort.

All data for subjects in each SAD cohort collected up to and including the 30-hour samples postdose will be evaluated for safety and tolerability before opening the next higher dose cohort. In each MAD cohort, data for subjects up to and including the 24-hour timepoint post morning dose on Day 8 will be evaluated for safety and tolerability before opening the next higher dose cohort. The dosing schedule may be extended if additional observations are needed at a particular cohort. In the absence of unacceptable AEs, the CRC may decide to open the next

cohort before having reviewed data from all of the evaluable subjects who have completed Day 7 in the SAD cohorts and Day 14 in the MAD cohorts.

Dose: This study employs a SAD followed by a MAD design. Part A Cohort 1 will initially evaluate a low dose of KNX100 (5 mg). For the following cohorts (2-4), the KNX100 dose will be increased as agreed by the CRC up to a maximum of 50 mg of KNX100 (Table 3) or to the maximum exposure level defined in Section 6.20.1, whichever occurs first. In Part B (MAD), dosing will initially evaluate a low dose of 10 mg, followed by a high dose to be selected based on safety, tolerability and exposure data generated in Part A. Cohort 3 of Part B will evaluate twice daily (b.i.d) dosing. The dose will be selected based on PK data from the preceding cohort. KNX100 and placebo will be encapsulated in identical size 0 capsules to ensure blinding of study treatment. Additionally, subjects assigned to receive placebo will have the same number of capsules as subjects receiving KNX100. Predefined stopping rules are provided to ensure the safety of all study subjects are defined in Section 6.20.

Control: A matching placebo control will be administered to evaluate treatment-related effects.

Population: KNX100 has not been previously administered to humans; therefore, its effects in humans are as yet unknown. A healthy volunteer population with carefully considered inclusion/exclusion criteria will avoid the potential for interaction of KNX100 with any underlying disease state or concomitant medication that it may be necessary for subjects to take, while ensuring that subjects are fit and well enough for participation in the study. Females of child-bearing potential will have to undergo a pregnancy test prior to enrollment.

3.2.1. Starting Dose Justification

Animal doses (intraperitoneal [IP] and oral) assessed in primary pharmacology models were used to predict the human efficacious dose of oral KNX100. The efficacious doses administered to mice were converted to human dose equivalents per the *FDA Guidance for Industry: Estimating the Maximum Safe Starting Dose in Initial Clinical Trials for Therapeutics in Adult Healthy Volunteers (July 2005)*.

Extensive preclinical efficacy data for the target indication of opioid withdrawal has been obtained using IP injection in mice. However, to date, preclinical efficacy data following oral administration in an opioid withdrawal mouse model is unavailable. The data collected in efficacy studies evaluating the effects of KNX100 (IP) on naloxone induced opioid withdrawal models in C57BL/6 mice and KNX100 (PO) in nicotine withdrawal models allow for a reasonable estimation of an effective dose range in humans, assuming allometric scaling on a mg/kg basis and similar affinities of KNX100 to pharmacodynamic (PD) targets in humans and C57BL/6 mice. Based on the available animal data, a pharmacologically effective dose range (PAD) of approximately 0.89-1.78 mg/kg of KNX100 phosphate (equivalent to 53-107 mg/day in a 60 kg adult) was anticipated for reducing the symptoms of opioid withdrawal in humans.

The human PK parameter estimates for CL/F and V/F based on single dose preclinical data from mouse, rat, and dog studies following oral administration was predicted using multiple allometric scaling approaches. Overall, the range of doses using multiple methods of prediction ranged from 53 to 125 mg. However, clearance in the rodent was much lower than in human, resulting in higher exposure levels that would not be achieved at the 53 or 125 mg doses. The AUC following a 3.7 mg/kg IP dose in the mouse was 23.3 h*ng/mL. Using the observed human CL/F value of 356,000 mL/h, a dose required to achieve the target AUC can be obtained using the following equation: $\text{Dose (ng)} = \text{CL (mL/h)} \times \text{AUC (h} \times \text{ng/mL)}$. Using this formula, a total daily dose of 8.3 mg was derived. However, the C_{max} following the 3.7 mg/kg IP dose was 45.5 ng/mL. Based on the clinical data already obtained, a dose of around 20 mg could be estimated to achieve a C_{max} of 46 ng/mL.

The NOAEL reported in the 28-day repeat dose toxicology studies in rat and dog (Beagle) was 50 mg/kg/day in rat and 15 mg/kg/day in dog which is equivalent to a human equivalent dose (HED) of the free base equivalent of 8.1 mg/kg/day and 8.3 mg/kg/day, respectively. Based on a maximum recommended starting dose (MRSD) of 1/10th of the NOAEL and using the most conservative approach, an MRSD of 0.81 mg/kg of free base which is equivalent to 1.2 mg KNX100 phosphate per kg per day. Assuming an average human weight of 60 kg, this would equate to a clinical starting dose of ~72 mg/day.

However, the severity, reversibility, and monitorable nature of the toxicity defining the NOAEL impacts how it influences the selection of the safe starting dose. Respiratory effects (decreased tidal and minute volume premonitory to decreased respiration rate in the rat) and central nervous system (CNS) effects (decreased body temperature and hypoactivity premonitory to convulsions in the rat; tremor, ataxia and hypoactivity premonitory to convulsions in the dog) both inform the selection of the safe starting dose. The severity of the CNS effects and trend towards greater-than-dose-proportional KNX100 exposure suggest a minimum of a 10-fold dose margin relative to the CNS effect threshold is appropriate to be protective of patient health. CNS effects, therefore, serve as the primary basis for selection of the starting and escalating clinical dose regimens.

The selection of the starting dose for human studies was based on the CNS NOEL determined in the 28-day dog toxicology study. In the dog, the CNS NOEL dose (7.5 mg free base/kg) corresponded to a HED of 6 mg KNX100 phosphate/kg. Therefore, 1/10th of this value is equivalent to 0.6 mg KNX100 phosphate/kg, or 36 mg KNX100 phosphate in a 60 kg subject which would be the maximum recommended starting dose.

However, due to observation of convulsions and other CNS effects in the toxicology studies, Kinosis commenced dosing at a dose lower than the calculated MRSD. Kinosis defined the FIH starting dose as 5 mg KNX100 phosphate in a 60 kg subject. This starting dose is a more conservative dose than the toxicology program directs and predicted a C_{max} of 50 ng/mL and an AUC₀₋₂₄ of 125 ng×hr/mL, which is approximately 30-fold lower than the exposure at the CNS NOEL in dogs, approximately 60- 90-fold lower than the exposure at which convulsions were observed in dogs. Based on the allometric body surface area (BSA) scaling approach, this starting dose was ~75-fold lower than the HED of the dog NOEL for convulsions reported in the 28-day toxicology study, 150-fold lower than the HED of the NOAEL in rats and dogs, and 250-fold lower than the dog LOEL for convulsions reported in the 28-day toxicology study.

Based on predictive modelling, the proposed starting dose of 5 mg was anticipated to achieve a maximum plasma concentration of approximately 50 ng/mL, well below the applied exposure cap. Subsequent clinical doses will be established based on scaling of the exposure results from the 5 mg dose.

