
Planned Number of Patients: Approximately 64 healthy subjects will be randomized for study participation. The total number of subjects will depend on the number of dose levels assessed during dose-escalation to determine the Recommended Phase 2 dose (RP2D) of KNX100.
 
Randomization will be controlled either via a list or Interactive Web Response System.
	

Diagnosis and Main Criteria for Inclusion: This study will evaluate healthy volunteers (male and female) who are between 18 and 55 years of age (inclusive) with a body mass index (BMI) of 18-32 (inclusive). Subjects must be willing to comply with study requirements and must agree to abstain from consuming alcohol or using recreational drugs. Subjects with specific underlying conditions (e.g., mental illness, human immunodeficiency virus (HIV), hepatitis, cardiovascular disease) or any medical history that would jeopardize their safety cannot participate. Additionally, subjects with clinically significant electrocardiogram (ECG),
	

electroencephalogram (EEG), physical examination, or laboratory findings will not be enrolled. Female subjects of childbearing potential must be willing and able to use defined methods of contraception throughout the study and for 30 days after the final follow-up visit.

Test Product; Dose; and Mode of Administration: KNX100 will be provided in capsule form as 5, 25 or 100 mg capsules for oral administration. Study drug will be encapsulated in hydroxypropyl methylcellulose (HPMC) dark green opaque size 0 capsules and packaged in 100 mL high density polyethylene (HDPE) bottles with polypropylene twist-off closures. Dosing will be based on the assigned treatment group. This study will evaluate doses of KNX100 starting with a single ascending dose (Part A, SAD) of 5 mg, increasing up to a maximum of 50 mg and a multiple ascending dose (Part B, MAD) starting at 10 mg and increasing up to 35 mg per dose, as tolerated. Individual doses will be dispensed by unblinded site pharmacy staff. Dose escalation will progress upon CRC approval. Subjects will take the study drug in the morning after an overnight fast. For subjects enrolled into MAD Cohort 3, subjects will take study drug in the morning after an overnight fast and again, approximately 8 hours after the first dose following a 2-hour fast.

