3.2.2. Maximum Dose

An upper limit of 35 mg per day is supported by the nonclinical data and human PK data, specifically by exposure at the 1/10th of the NOEL of 2.75 mg/kg established in the 14-day dog EEG study, however this will be guided by emerging safety and PK data. Dose escalation will stop at any time if unacceptable safety findings are identified or if the maximum concentration (C_{max}) or area under the curve (AUC) exceeds or is likely to exceed 1/10th of the exposure associated with the NOEL of 2.75 mg/kg seen in the 14-day dog EEG study (84.9 ng/mL or 82.7

h×ng/mL for KNX100 and 26.5 ng/mL and 45.7 hr × ng/mL for KNX100A, respectively). In this case, the CRC may stop the study, or modify the dose downwards in subsequent cohorts.

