5.2. Treatments Administered

Both KNX100 and placebo will be administered orally based on the assigned treatment group (refer to [Section 5.3](#)). For each cohort, a total of 8 subjects will be dosed (6 with KNX100 and 2 with placebo).

Part A will evaluate doses of KNX100 starting with 5 mg and increasing up to a maximum of 50 mg per day ([Table 3](#)). Doses post the 5 mg dose will be decided by the CRC upon review of all available data.

Part B will evaluate a low- (10 mg), and high-dose, based on the doses evaluated in Part A and the safety, tolerability, and PK of doses in the previous cohorts, administered for 7 consecutive days ([Table 4](#)). Part B (Cohort 3) will evaluate twice daily dosing of a single dose, selected based on the safety, tolerability, and PK of doses in the previous cohorts, administered for 7 consecutive days ([Table 4](#)).

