5.3.1. Sentinel Subject Review and Toxicity Management

Part A Cohorts 1 through 4 will initiate dosing with 2 sentinel subjects who are randomly assigned so that 1 subject receives KNX100 and the other receives placebo. Following dosing of study medication, site personnel will observe the sentinel subjects for 48 hours, at which time the investigator will review the safety and tolerability for both sentinel subjects. This will include housing of the sentinel subjects in the Phase 1 unit for 30 hours postdose and then a follow up phone call at approximately 48 hours postdose administration.

Data reviewed will include AEs, clinical laboratory results, vital signs, and ECGs, EEGs, and PK parameters for both subjects. PK will be evaluated to ensure that exposure has not exceeded the maximum clinical exposure cap defined in [Section 6.20.1](#). Upon acceptance of reviewed data by the site and CRC, dosing may continue for the remaining 6 subjects. The investigator will document the review and decision by email to Sponsor representatives.

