5.3.4. Dose Escalation

An evaluable subject is one that has been dosed, completed all assessments, and had their data reviewed by the CRC.

Blinded data to be reviewed by the CRC for each subject will include (as a minimum): PK (up to 30 hours postdose for Part A and 24 hours postdose for Part B), EEG, ECG, vital signs, pulse oximetry, neurological examination, and any adverse events.

The CRC may approve dose escalation following review of cohort data if:

- No drug related SAE's occurring within 48 hours of administration of KNX100 or placebo is observed in any subject in the dose group under evaluation.
- No drug related AE's of Grade 3 or greater are observed in 2 or more subjects within a dose group.
- The mean KNX100 C_{max} **OR** AUC does not exceed 84.9 ng/mL or 82.7 ng×h/mL respectively **and** the mean KNX100A C_{max} **OR** AUC does not exceed 26.5 ng/mL and 45.7 hr × ng/mL, respectively, the exposure associated with 1/10th of the NOEL of 2.75 mg/kg observed in the 14-day dog EEG study.
- No emergence or evidence of other PI-deemed and or medical monitor-deemed clinically significant abnormal vital signs, neurological and physical examination, or safety parameters postdose have been observed.

Dose increases will be permitted once review of data from all evaluable subjects has been performed.

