6.20.2. Maximum Tolerated Dose Definition

The maximum tolerated dose (MTD) is defined as the dose below a non-tolerated dose and therefore can only be determined by the observation of a dose level, which is no longer considered acceptable in healthy subjects.

In this study, a dose will be considered non-tolerated and dose escalation will cease if 2 or more subjects in a cohort experience an AE of Grade 3 or higher occurring within 48 hours of administration of KNX100 or placebo at the dose level. Once the non-tolerated dose is defined,

the MTD will be confirmed at the previous dose level below the non-tolerated dose, or a dose between the non-tolerated dose and the last tolerated dose may be investigated. If the dose-escalation scheme is successfully completed for all escalating doses, 35 mg/day will be the highest dose studied (refer to [Section 5.3.2](#) and [Section 5.3.3](#) for the dosing schedule).

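### On the protocol's own CL/F, the 50 mg single dose, and 30 mg b.i.d. if the cap is per day, project above the AUC cap; the mg ceilings conflict, and the Section 5.3.4 checklist has no forward-looking exposure test

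*Protocol*

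**What the plan says.** **Exposure.** Protocol Section 3.2.1 states: "Using the observed human CL/F value of 356,000 mL/h, a dose required to achieve the target AUC can be obtained". It sets dose equal to CL times AUC and also puts a Cmax of 46 ng/mL at around 20 mg. Section 6.20.1 caps KNX100 at Cmax 84.9 ng/mL and AUC0-last 82.7 h·ng/mL, with separate limits for KNX100A.

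**Dose ceilings.** Section 3.2.2: "An upper limit of 35 mg per day is supported by the nonclinical data and human PK data". Section 6.20.2: "35 mg/day will be the highest dose studied". Section 5.2, for Part A: "increasing up to a maximum of 50 mg per day". The Synopsis, for Part B: "starting at 10 mg and increasing up to 35 mg per dose, as tolerated". Table 3 lists 50 mg for Cohort 4. Table 4 lists 30 mg twice daily for Cohort 3, which is 60 mg/day.

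**Escalation tests.** Section 3.2.2 stops escalation if Cmax or AUC "exceeds or is likely to exceed 1/10th of the exposure associated with the NOEL of 2.75 mg/kg" in the dog EEG study. Section 5.3.4 lets the CRC approve the next dose if, among other conditions, the mean KNX100 Cmax or AUC "does not exceed 84.9 ng/mL or 82.7 ng×h/mL respectively", with a matching condition for KNX100A. For the Part A sentinels, Section 5.3.1 says: "PK will be evaluated to ensure that exposure has not exceeded the maximum clinical exposure cap".

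**The concern.** Section 6.17.5 names exposure monitoring, together with EEG, as the mitigation for seizure risk in these healthy volunteers. The cap therefore needs to work before a dose is given. A CRC working from the Section 5.3.4 list applies a weaker test than Section 3.2.2 and finds mg ceilings that cannot all be true. If nobody projects exposure at the next dose, an excess would first be seen in the Part A sentinels, of whom one receives active drug, and that check also looks back at exposure already reached. Section 5.3.1 provides no sentinel step for Part B.

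**Working it through.** **Inputs.** CL/F 356,000 mL/h, the mouse AUC of 23.3 h·ng/mL, and Cmax 46 ng/mL at about 20 mg (Section 3.2.1). KNX100 caps of 82.7 h·ng/mL and 84.9 ng/mL (Section 6.20.1). Planned doses from Tables 3 and 4. Free-base content of 67.1 mg per 100 mg phosphate (Table 2), so a factor of 0.671.

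**Step 1: the plan's own figure.** 356,000 × 23.3 = 8,294,800 ng = 8.3 mg, as stated.

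**Step 2: dose at each cap.**
- AUC: 356,000 × 82.7 = 29.4 mg. If CL/F was computed on free base, 29.4 / 0.671 gives 43.9 mg of phosphate.
- Cmax: 46 / 20 = 2.3 ng/mL per mg, so 84.9 / 2.3 = 36.9 mg.

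**Step 3: planned doses.** AUC = dose / 356,000, multiplied by 0.671 for the free-base case. Cmax = 2.3 × dose. Multiples of the cap are in brackets.

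| Dose | AUC, phosphate basis | AUC, free-base basis | Cmax |
|---|---|---|---|
| 25 mg | 70.2 (0.85) | 47.1 (0.57) | 57.5 (0.68) |
| 30 mg once daily | 84.3 (1.02) | 56.5 (0.68) | 69.0 (0.81) |
| 35 mg | 98.3 (1.19) | 66.0 (0.80) | 80.5 (0.95) |
| 50 mg | 140.4 (1.70) | 94.2 (1.14) | 115.0 (1.35) |
| 30 mg b.i.d., per day | 168.5 (2.04) | 113.1 (1.37) | 69.0 per dose (0.81) |

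The b.i.d. row ignores carry-over between doses. At 30 mg once daily the projection is too close to the cap to call an excess.

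**Step 4: AUC0-last against AUC0-∞.** CL/F corresponds to AUC0-∞, while the cap is AUC0-last. The extrapolated share of AUC0-∞ that would bring each dose down to the cap is 1 − 82.7 / AUC:
- 50 mg: 1 − 82.7/140.4 = 41% (phosphate); 1 − 82.7/94.2 = 12% (free base).
- 60 mg/day: 1 − 82.7/168.5 = 51% (phosphate); 1 − 82.7/113.1 = 27% (free base).

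The Cmax excess at 50 mg does not depend on this.

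**Step 5: ceilings.** 50/35 = 1.43 and 60/35 = 1.71 times the 35 mg/day limit. The Synopsis limit of 35 mg per dose, given twice daily, would be 70 mg/day.

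**Step 6: the checklist.** A 25 mg cohort projects to an AUC of about 70, which meets the Section 5.3.4 exposure condition while Table 3 lists 50 mg next. The test in Section 3.2.2, applied to that next dose, would stop or reduce it.

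**Step 7: AUC basis for Cohort 3.** SAP Table 4 (Section 6.3.1) derives AUC0-last over the whole profile, covering both doses, and also AUC0-8h and AUC8-16h. Neither document says which is compared with the cap. The protocol leans towards per day: Section 3.2.1 derives a total daily dose from an AUC, and Section 3.2.2 pairs the cap with a daily mg limit.

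**The case against.** The strongest reply is that the protocol does not authorise any dose that breaches the cap. Section 3.2 limits Part A to 50 mg or the exposure cap, whichever is reached first. Section 3.2.1 sets later doses by scaling exposure from 5 mg. Sections 3.2.2, 5.3.3 and 6.20.1 all hold dosing to the cap, and the table footnotes make the doses provisional. Meeting Section 5.3.4 does not cancel those provisions, and the CRC Plan (Section 9.8), which is not available here, may add detail. This stands as far as it goes: a cap exists, and Section 5.3.4 is weaker than the text around it rather than the only control. It does not explain why the approval checklist omits a test required elsewhere, and it does not reconcile 50 mg, stated as a maximum in Section 5.2, with a highest dose of 35 mg/day.

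The second reply is that the larger multiples are upper-end. Section 3.2.2 says human PK data support 35 mg/day under this cap, yet on the phosphate basis 35 mg projects to 1.19 times the AUC limit. Either that statement is also wrong, or the phosphate projection overstates exposure. On free base, 35 mg fits (0.80), the 50 mg AUC excess is only 14%, and a 12% extrapolated share would remove it. This is a fair limit on the size. The 50 mg Cmax excess remains, although it comes from proportional scaling of one approximate figure.

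Third, the b.i.d. excess depends on a per-day reading, and 30 mg b.i.d. respects the Synopsis limit per dose. That is correct, and it is why the basis has to be stated.

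Finally, Section 3.2.1 shows that dosing had begun, and the documents do not say which cohorts were complete. Changing Table 3 may have little forward effect, but the Part B rules would still need the correction.

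**Conclusion.** The concern holds. The conflict between ceilings (35 mg/day, 35 mg per dose, 50 mg, 60 mg/day) and the missing forward-looking test in Section 5.3.4 are plain on the text and need no PK assumption.

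The projected excess is conditional. At 50 mg it is 1.14 to 1.70 times the AUC cap, depending on salt basis, and 1.35 times the Cmax cap. At 30 mg b.i.d. it is 1.37 to 2.04 times the AUC cap, on a per-day reading only, with Cmax inside its limit. No excess is claimed at 30 mg once daily.

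These are point projections under linear PK from one CL/F value given without dose, spread or salt basis, and the AUC figures are also subject to the extrapolation limits in Step 4. Section 3.2.1 reports a nonclinical trend to more than dose-proportional exposure; if it held in humans, the projections would be too low. KNX100A cannot be projected from the documents.

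**What to change.** Add a criterion to Section 5.3.4:

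> The projected mean Cmax and AUC0-last of KNX100 and KNX100A at the proposed next dose do not exceed the Section 6.20.1 limits; the projection is documented at the CRC review before the cohort opens.

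Then:
- Reconcile Tables 3 and 4 and the 35 mg/day, 35 mg per dose and 50 mg ceilings with the cap and with each other. Aligning everything to 35 mg would not be enough by itself, because on the phosphate basis 35 mg projects above the AUC cap.
- State whether the AUC cap applies per dose or per day in the b.i.d. cohort, and which SAP parameter is compared with it.
- State whether CL/F refers to phosphate or free base.

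Which dose or limit is right is for the sponsor to decide. The cost is amendment wording and one projection per CRC review from PK data already in the package. The downside is that some planned doses may be lowered.
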